Each step of DICE will be documented by the ODC in their clinic note within the EMR as is part of usual practice. In the “Describe” step, the ODC will obtain an accurate characterization of the behavior and the context in which it occurs as well as quantify the frequency and severity of the most troublesome behavior (as defined by the care partner) using the one-item question we have used in prior trainings (16, 17): “Please rate from 0 to 4 the severity and frequency of the behavior (0=none or never; 1=mild and/or occasionally; 2=moderate and/or sometimes; 3=severe and/or frequently; and 4=very severe and/or daily). If the severity and frequency are different, pick the higher score (e.g. a behavior that is daily but mild should be scored as a 4)”. In the “Investigate” step, the ODC will identify possible underlying and modifiable causes of the behavior.

With information obtained in the “Describe” and “Investigate” steps, the ODC will work with the care partner to create and implement a treatment plan to manage BPSD. The ODC will brainstorm with the care partner (e.g. what are activities the PLWD enjoys) and instruct the care partner in behavioral and environmental strategies. These approaches could include enhancing effective communication with the PLWD, creating meaningful activities, dealing with environmental challenges including ensuring safety, and simplifying tasks and creating structured routines. The ODC will also consult with other relevant clinic personnel on the Create treatment plan as needed; for example, a plan may involve having the provider assess and manage infection, constipation or pain. From prior experience with DICE, these first three steps (Describe, Investigate, Create) can be accomplished in 30 minutes.

Following the “Create” step, and in a 2-week follow-up contact by telephone, the ODC will engage in the “Evaluate” step with the care partner, during which the ODC will determine if recommended strategies were used and their effectiveness. Effectiveness will be measured by repeating the frequency/severity question asked of the care partner in Describe so that the impact of the strategy can be assessed quantitatively comparing the pre- and post-strategy scores at 2 weeks’ time; any downward movement of the score will be categorized as effective. If the DICE generated strategies were effective, the ODC will monitor and surveil for BPSD with monthly contact. If the DICE generated strategies were not effective, the ODC will

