6.2.3 Follow-up Visits

Visits will be flexible and tailored to the needs of each care partner and PLWD as part of usual care. However, in general, Visit 1 will consist of meeting with the care partner over the phone to determine if any behavioral or psychological symptoms of dementia (BPSD) are present. If none are present, the ODC will educate the care partner about BPSD and the DICE Approach and create a plan for monitoring during the 6-month study period. If BPSD are present, the “Describe” and Investigate” steps of the DICE intervention will be triggered. Using this information during the same visit, the ODC will work with the care partner to create and implement a treatment plan. This visit will be accomplished in 30 minutes. Visit 2 will occur approximately 2 weeks after the first visit. The ODC will engage in the “Evaluate” step to determine if the treatment plan was implemented and its effectiveness. If effective, the ODC will monitor and surveil for BPSD with monthly contact. If not effective, the ODC will work with the care partner to create additional treatment strategies and then follow up at intervals between 2 weeks and 1 month as needed.

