7.3 Adverse Events and Serious Adverse Events

Adverse Event (AE): Any untoward or unfavorable medical occurrence in a clinical research study participant, including any abnormal sign (e.g. abnormal physical exam or laboratory finding), symptom, or disease, temporally associated with the participants' involvement in the research, whether or not considered related to participation in the research.

Serious Adverse Event (SAE): Any adverse event that:

- Results in death
- Is life threatening, or places the participant at immediate risk of death from the event as it occurred
- Causes persistent or significant disability or incapacity
- Results in congenital anomalies or birth defects
- Is another condition which investigators judge to represent significant hazards

No AE's or SAE's are expected based upon the study intervention. Hospitalizations and ED visits are secondary outcomes in the study and not considered adverse events. However, we will collect data on such events from the medical chart and caregiver report during visits and report them as needed.

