9.4 Outcomes

Clinical outcomes: all UCD clinical sites (inpatient and outpatient) use the same EMR (EPIC), so ascertaining clinical outcomes will be uniform across clinics. The primary clinical outcome is the feasibility of measuring psychotropic medication use. Mean PLWD participant

psychotropic medication use during the intervention period will be compared to historical controls (mean rate of medication use among PLWD for the four participating clinics in the 6 months prior to the intervention). Secondary clinical outcomes will be the feasibility of measuring rates of hospitalizations, ED visits and nursing home placement ascertained from the EMR. Mean PLWD participant health care utilization during the intervention period will be compared to historical controls (mean rate in the 6 months prior to the intervention). The feasibility of obtaining the nursing home placement variable from the EMR will be established during this pilot study by ascertaining nursing home placement from care partners and then determining if it subsequently is recorded in the EMR.

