9.5 Data Analyses

Data will be summarized with descriptive statistics to allow us to review the demographics and clinical characteristics of our enrolled participants, as well as to review implausible values. The extent of missing data will also be assessed as a key indicator of feasibility of collecting data from clinic notes and the EMR; additionally, we will ascertain whether baseline characteristics are associated with missingness in order to modify study procedures for the larger trial. Feasibility will be characterized by rate of enrollment (# enrolled/# invited to enroll), number of contacts between ODCs and dyads (summarized as averages/SDs across dyads), and time requirements (summarized as averages/SDs). We will examine these overall and by clinic, to ensure consistency across clinics. We will summarize data on medication use (binary: psychotropic use or not) for the four clinics overall prior to the study and for enrolled PLWD post-intervention and will compare them using mixed models with a logit link to analyze these pre-post data, accounting for correlation within clinic. Models will first be fitted in a crude fashion, secondarily we will include covariate adjustment as a means to inform design characteristics in the ePCT, recognizing we have limited power to make definitive conclusions from these analyses. We will similarly examine healthcare utilization (counts of hospitalizations and ED visits; binary measure of nursing home placement) once we ensure that these data are feasibly collected from the EPIC EHR.

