10 DATA COLLECTION AND QUALITY ASSURANCE

10.2 Data Collection Forms

Data will be collected from the electronic medical record. ODCs will put information about the use of the DICE Approach into their routine clinical notes. Exit interviews will be collected on paper and uploaded into secure study files.

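### The nursing-home check in 9.4 runs one way only and does not say whether ODC notes count as the EMR record

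*Combined protocol and SAP*

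**What the plan says.** Under 9.4 the secondary clinical outcomes are the "feasibility of measuring rates of hospitalizations, ED visits and nursing home placement ascertained from the EMR". For placement, feasibility is to be established by "ascertaining nursing home placement from care partners and then determining if it subsequently is recorded in the EMR". Aim 2 in the Précis describes the same check. Participants are then compared with historical controls from the six months before the intervention. In 9.5 the variable is a "binary measure of nursing home placement", examined in the same way as medication use once its collection has been shown to be feasible.

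The contacts and records around this check are as follows:

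- **Contacts.** After a first call and a follow-up at about two weeks, 6.2.3 says that, if the strategies worked, "the ODC will monitor and surveil for BPSD with monthly contact". If they did not, the ODC follows up at intervals of two weeks to a month.
- **ODC notes.** Section 5.1 says "Each step of DICE will be documented by the ODC in their clinic note within the EMR as is part of usual practice". Section 10.2 says "Data will be collected from the electronic medical record. ODCs will put information about the use of the DICE Approach into their routine clinical notes".
- **Adverse events.** Section 7.5 lists nursing home placement as an adverse event and says events may surface at ODC visits or in chart review. Events are entered in an on-line system.
- **Schedule.** The table in 6.1 marks nursing home placement only at Visit 7 (Day 164).
- **Historical controls.** Section 4.1 requires only a chart diagnosis of dementia, and 6.2.1 describes EMR access under a waiver. No care-partner contact is described for them.

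The plan does not say who asks the care partner about placement, where the answer is kept, which parts of the EMR are searched, or what result counts as feasible.

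**The concern.** Aim 2 asks whether the EMR can supply the outcomes for a later full-scale trial, so a check of EMR accuracy is central to it. The stated check covers half of that question. It starts from placements the care partner reports and looks for them in the EMR. It never starts from an EMR placement and asks whether it is true. A short rehabilitation stay coded as a placement would go unnoticed.

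The second difficulty is independence. If the report reaches the ODC and the ODC notes it in the EMR, the search can find that note and count the placement as captured. The check also looks for a record made after the report, which is when such a note would appear. The capture rate would then partly describe the study's own documentation. If the same entries also count as the outcome, participants have a route into the EMR that is not described for historical controls.

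**Working it through.** **1. The plan's own figure.** None is given for this check. The only precision figures are the 95% interval widths for a 75% enrollment rate in 9.1. Exact intervals reproduce them (17.8% at n=100 against the stated 18%; 36.2% at n=25 against 36%), but they do not bear on placement.

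**2. What the check can estimate.** Cross-classify participants by care-partner report and EMR record:

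| | In EMR | Not in EMR |
|---|---|---|
| Reported | a | b |
| Not reported | c | d |

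The plan yields a/(a+b), which is sensitivity against the care partner's report. Cell c is never examined, so a/(a+c), the share of EMR placements that the care partner confirms, is unknown. If c were as large as a, half the EMR placements would be unconfirmed and the plan's figure would not change.

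**3. Whether ODC notes can enter the search.** Sections 6.2.3 and 7.5 make an ODC contact a likely place for a placement to be mentioned. Sections 5.1 and 10.2 put ODC notes in the EMR and make the EMR the data source. No section excludes those notes from the search. Equally, no section says that the ODC records placement.

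**4. Size of the possible bias.** Let s be the share of true placements that routine EMR entries capture. Let k be the share of the remainder that enters the EMR only through ODC notes. Neither is in the documents, so both are assumed. With equal true placement rates:

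- apparent capture in participants = s + (1 − s)k
- apparent ratio, participants to controls = [s + (1 − s)k]/s

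| s | k = 0 | k = 0.5 | k = 1 |
|---|---|---|---|
| 0.9 | 1.00 | 0.95/0.9 = 1.06 | 1/0.9 = 1.11 |
| 0.7 | 1.00 | 0.85/0.7 = 1.21 | 1/0.7 = 1.43 |
| 0.5 | 1.00 | 0.75/0.5 = 1.50 | 1/0.5 = 2.00 |

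At s = 0.4 and k = 1 the ratio would be 2.50. Any excess above 1.00 counts against DICE. Apparent capture moves too: at s = 0.5 it reads 50%, 75% or 100% for k = 0, 0.5 or 1.

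**5. Precision.** The number of placements is not given. As illustrations, 8 of 10 found gives an exact 95% interval of 44% to 97%, and 5 of 5 gives 48% to 100%. The capture rate will be imprecise under either definition. This is a separate limit, which the fix does not remove.

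**The case against.** A reader might infer that the check is circular, that capture is biased upward, and that the pre-post comparison is biased against DICE. The documents do not support these as facts:

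- Sections 5.1 and 10.2 speak of DICE steps and use of the approach, not of placement.
- The report could come from elsewhere. Study team members conduct the exit interviews with care partners (6.2.4), and the event system in 7.5 is described separately from the EMR. However, the plan assigns the check to neither, and 6.2.4 describes the interviews as covering acceptability and implementation.
- The compared outcome is defined as taken from the EMR, so the care-partner report is a validation source. Bias arises only if ODC-prompted entries, or the reports themselves, are counted.
- Section 4 describes the provider handoff as current standard of care, and 5.1 calls ODC documentation usual practice. Some comparable notes may exist for the earlier period, which would narrow the gap.

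These points stand, and they reduce circularity and unequal ascertainment to risks that the plan leaves open. They do not answer the one-directional design, which is plain in 9.4.

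A reader might also extend the point to hospitalizations and ED visits, because 7.3 says "we will collect data on such events from the medical chart and caregiver report during visits". That sentence concerns those two event types only, and it deals with safety reporting. Section 9.4 says all UCD inpatient and outpatient sites share one EMR, and nothing suggests that the outcome counts come from ODC notes. The extension is too weak to make.

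Finally, ODC notes would be ordinary EMR content wherever the programme is embedded, so discarding them outright would answer a different question. That argues for reporting both figures.

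**Conclusion.** The check measures sensitivity only; this follows directly from the text. In addition, the capture rate could be raised by the study's own notes, and the comparison with historical controls could be biased against DICE. Both depend on ODC-prompted entries being counted, which the plan neither states nor excludes. With equal true rates, the apparent ratio is 1.00 if ODC notes add nothing. It is about 1.1 to 2.0 if they give near-complete capture and routine capture is an assumed 90% to 50%.

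A reader might go further and say that the capture rate cannot carry over to the full-scale trial. That presumes a comparison group without ODC contact, and the documents do not describe that trial's control design. The narrower statement is that capture from non-ODC sources is the figure that does not depend on ODC contact.

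Importance is minor to moderate. The check serves Aim 2 and precedes the utilization analysis in 9.5. But placement is a secondary pilot outcome, it is not one of the two progression criteria, and 9.5 already acknowledges limited power.

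**What to change.** Amend 9.4 as follows:

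1. Name who obtains the care partner's report and where it is stored outside the EMR. The placement assessment already scheduled at Visit 7 is the natural occasion.
2. Cross-tabulate report against EMR record in both directions: reported placements found in the EMR, and EMR placements confirmed by the care partner. Accept EMR entries made before or after the report, within a stated search window.
3. Report capture with and without placements found only in ODC/DICE notes. Let the non-ODC figure inform the full-scale trial.

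In 9.5, use the same non-ODC EMR sources (for example the address or facility field, discharge disposition, and notes by other clinicians) for participants and historical controls in the placement comparison.

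The cost is protocol wording, one extraction rule and slightly more extraction work. Measured capture may be lower than if ODC notes were counted.

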9.5 Data Analyses

Data will be summarized with descriptive statistics to allow us to review the demographics and clinical characteristics of our enrolled participants, as well as to review implausible values. The extent of missing data will also be assessed as a key indicator of feasibility of collecting data from clinic notes and the EMR; additionally, we will ascertain whether baseline characteristics are associated with missingness in order to modify study procedures for the larger trial. Feasibility will be characterized by rate of enrollment (# enrolled/# invited to enroll), number of contacts between ODCs and dyads (summarized as averages/SDs across dyads), and time requirements (summarized as averages/SDs). We will examine these overall and by clinic, to ensure consistency across clinics. We will summarize data on medication use (binary: psychotropic use or not) for the four clinics overall prior to the study and for enrolled PLWD post-intervention and will compare them using mixed models with a logit link to analyze these pre-post data, accounting for correlation within clinic. Models will first be fitted in a crude fashion, secondarily we will include covariate adjustment as a means to inform design characteristics in the ePCT, recognizing we have limited power to make definitive conclusions from these analyses. We will similarly examine healthcare utilization (counts of hospitalizations and ED visits; binary measure of nursing home placement) once we ensure that these data are feasibly collected from the EPIC EHR.

Models will first be fitted in a crude fashion, secondarily we will include covariate adjustment to inform design characteristics in the ePCT, recognizing we have limited power to make definitive conclusions from these analyses. We will similarly examine healthcare utilization (counts of hospitalizations and ED visits; binary measure of nursing home placement) once we ensure that these data are feasibly collected from the EPIC EHR. In order to go on to the ePCT, we must meet two criteria. First, the primary feasibility outcome (enrollment rates) must be greater than 75%. Second, we must be able to show that the lower limit of the 90% confidence interval for testing the pre-post medication use is greater than a 25% decrease in the pre-study proportion. The former criteria is based on the observed enrollment rate in the pilot from the WeCareAdvisor study (17) of PLWD-care partner dyads; the latter is based on what is reasonable to assume will change in the shorter 6-month pilot and is clinically relevant.

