4 SELECTION AND ENROLLMENT OF PARTICIPANTS

Study Population: English-speaking (as discerned from the EMR) PLWD-Care partner dyads from the 4 participating clinics will be recruited. Dyads in the participating clinics will be identified in the following way:

- via warm handoff from a clinic provider to the ODC via the current standard of care for working with caregivers of PLWD regarding behavioral concerns, ODCs will be notified of the potential study participant by either of the two methods of ascertainment by the study RA. The ODC will then contact the care partner who is identified in the EMR as the responsible person or family member for the PLWD by telephone participation in the DICE program. We will also track the proportion of PLWD without a caregiver listed for study tracking.

Setting: Participants will be recruited from four primary care clinics in the Primary Care Network (total of 13) at University of California Davis. Clinics have been selected for the number of PLWD seen annually in each clinic. Below is preliminary information obtained on the potential subject population for the four study clinics from FY 1/1/2021-12/31/2021:

	Midtown	Elk Grove	ACC	FCC
>65 years old Dementia	63	67	66	76
Race/ethnicity				
White	40 (63.55)	35 (52.2%)	40 (63.5%)	27 (35.5%)
Black	11 (17.5%)	14 (20.9%)	11 (17.5%)	11 (14.5%)
Asian	8 (12.7%)	10 (14.9%)	8 (12.7%)	25 (32.9%)
Other	4 (6.4%)	8 (11.9%)	4 (6.3%)	
				13 (17.1%)

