4.1 Inclusion Criteria

Participants must meet all inclusion criteria to participate in the study:

DICE participants

- 1) Person living with dementia (as defined by chart diagnosis) and their care partner
- 2) Care partner age >18 as defined in the EMR
- 3) Care partner English speaking

Historical controls

- 1) Person living with dementia (as defined by chart diagnosis)

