4.3 Study Enrollment Procedures

PLWD-Care partner dyads from the 4 participating clinics will be recruited via warm handoff from a clinic provider. The ODC will then contact the care partner who is identified in the EMR as the responsible person or family member for the PLWD by telephone to discuss participation in the DICE Program. Participants will be recruited from four primary care clinics in the Primary Care Network (total of 13) at University of California Davis. Clinics have been selected for the number of PLWD seen annually by clinic social workers who are embedded in each clinic. As a minimal risk study embedded in primary care practices, we plan to obtain a waiver of informed consent for PLWD, care partners and clinic staff in order to reduce introduction of artificial care resources or biases wherever possible. There will be minimal PHI data collected.

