5 STUDY INTERVENTIONS

5.1 Interventions, Administration, and Duration

This is a single group intervention. We have arranged with University of California Davis LVN supervisors to do a 6-hour training for all the LVNs on a single day. This will be a hybrid of in person (kick off session and ending brainstorming session) and watching the online modules together in a campus auditorium. ODCs will then use the approach in a “test” case in study months 2-3 during which they will engage in as needed coaching with a DICE trainer (a

geriatric psychiatrist and education specialist) to ensure they are using the approach with fidelity. Manualization and training with follow-up coaching have been shown to be effective implementation strategies that can enhance fidelity of implementation of an evidence-based program. Other clinic personnel (social workers and PCPs) will also receive the manual, an email overview of the study, and be invited to train using the website or at the on-site training. Following training and case consultation, the ODCs will then use the DICE Approach for any PLWD they encounter during the 6-month study period (months 4-9). Primary outcome metrics will be collected using the electronic medical record and by estimating time spent in the approach and strategies extracted from clinic notes.

As part of the DICE program, the ODC will meet with the PLWD-Care partner dyad by phone to determine if any BPSD are present. If no BPSD are currently present, the ODC will educate the care partner about DICE, including minimizing risk factors to prevent behaviors, and plan to continue monitoring (26) for BPSD during the 6-month study period. If BPSD are occurring, then the “Describe” and “Investigate” Steps of DICE will be triggered.

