6.2.1 Screening Evaluation

Consenting Procedure

Not applicable. A waiver of informed consent will be sought as DICE will be part of any contact by the ODC with care partners about behavioral concerns in the PLWD. A waiver of information consent will also be requested for access to the EMR for the historical controls.

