9 STATISTICAL CONSIDERATIONS

9.0 General Design Issues

The overarching goal of this proposal is to refine and pilot the application of DICE in primary care clinics by: (a) leveraging existing clinic staff to deliver DICE; and (b) using electronic resources to identify and recruit PLWD-care partner dyads based on clinically relevant and minimum inclusion/exclusion criteria. We maximize a pragmatic approach and minimize a separate study infrastructure to evaluate feasibility and acceptability in order to prepare for a larger embedded pragmatic trial (ePCT). Licensed practical nurses embedded in four primary care practices at University of California Davis (UCD), whom we will refer to as “Onsite DICE Coordinators” (ODC), will coordinate behavioral management using DICE with care partner-PLWD dyads and other clinic providers. We will accomplish this goal through the following specific aims:

Aim 1. To assess the feasibility and acceptability of the ePCT protocolized version of DICE that will guide the subsequent evaluation of the effectiveness of the intervention in a full-scale ePCT. DICE will be implemented in four large primary care clinics within the UCD Health System over a 6-month period (n=100 PLWD-care partner dyads; 25 dyads per site, allowing comparison of implementation and outcomes by site characteristics). Feasibility measures will include: 1) rate of subject enrollment (PLWD-care partner dyads); 2) number of contacts between ODCs and dyads; and 3) time requirements for ODCs implementing DICE. Acceptability will be measured by the acceptance rates of the ODC’s recommendations of strategies for BPSD (generated by use of DICE) among dyads, as well as other providers within the primary care practice. Exit interviews of participants (ODCs, other providers and care partners) will be conducted to further deepen the knowledge of intervention acceptability and implementation challenges.

Aim 2. To determine the feasibility of ascertaining and analyzing the primary (psychotropic medication use) and secondary clinical outcomes (hospitalizations, ED visits and nursing home placement of PLWDs) from the existing health system-wide electronic medical record (EMR) which will subsequently be used in a full-scale effectiveness ePCT. Clinical outcomes for PLWD participants will be measured after the 6-month DICE implementation period using the EMR and

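### The medication comparison behind the second progression criterion is labelled pre-post but sets enrolled participants against controls chosen by a looser rule, so a baseline gap of unknown sign and size enters the estimate

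*Combined protocol and SAP*

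**What the plan says.** Section 9.5 compares binary psychotropic use "for the four clinics overall prior to the study and for enrolled PLWD post-intervention and will compare them using mixed models" with a logit link, accounting for correlation within clinic. Models are fitted crude first. Covariate adjustment is secondary, and the covariates are not named.

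The same section sets two conditions for moving to the ePCT. The second is that "the lower limit of the 90% confidence interval for testing the pre-post medication use is greater than a 25% decrease" in the pre-study proportion. It does not say whether the crude or the adjusted model supplies the interval.

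The selection rules differ:

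- **Controls.** Section 4.1 lists one criterion: "Person living with dementia (as defined by chart diagnosis").
- **Participants.** Section 4.1 adds a care partner, who must be an adult and speak English. Section 4.3 says dyads "will be recruited via warm handoff from a clinic provider". Section 6.2.1 says "DICE will be part of any contact by the ODC with care partners about behavioral concerns in the PLWD".
- **No listed caregiver.** Section 4 says "We will also track the proportion of PLWD without a caregiver listed for study tracking". Such people can be controls but cannot be participants.

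The handoff is not described as the only route. Section 9.0 also speaks of "using electronic resources to identify and recruit PLWD-care partner dyads based on clinically relevant and minimum inclusion/exclusion criteria", and Section 4 mentions two methods of ascertainment. Dyads without symptoms stay in: "If no BPSD are currently present, the ODC will educate the care partner about DICE" (Section 5.1).

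The control group itself is defined in three ways. It is all PLWD in the four clinics in Section 1.1 and in Aim 2 of Section 9.0. It is 100 people with no selection rule in the Précis (Sample Size and Population) and in Section 3. Section 9.1 states both.

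**The concern.** A pre-post comparison normally lets people serve as their own controls. Here the before value belongs to a clinic-wide group and the after value to a selected subset. If participants already used psychotropics more or less often than the clinic average, that difference is counted as change. It can hide a real decrease or imitate one.

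Nothing in the analysis removes it. The model has a clinic term but no person term, so even participants who also appear among the controls contribute unlinked values. Their own earlier use is obtainable: Section 6.1 records current medications at screening and baseline, and the EMR is the data source.

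At stake is the decision to proceed to the full trial. The same contrast is planned for hospitalizations, ED visits and nursing home placement, but no progression rule rests on those.

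**Working it through.** **Plan's own figures.** The only precision figures are the 95% interval widths for a 75% enrollment rate in Section 9.1: 18% overall and 36% per clinic. Exact intervals reproduce them (17.8% at n = 100, 36.2% at n = 25). They concern enrollment and say nothing about the medication contrast, for which the plan gives no rate, power or precision.

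**Inputs.** From the documents: 100 participants; 63 + 67 + 66 + 76 = 272 PLWD in the Section 4 clinic table (over 65, 2021), used here as the size of an all-PLWD control group; a 90% interval; a 25% relative decrease. Assumed: clinic rate 42% (range 30% to 60%) and gaps of 3 and 10 points.

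**Step 1: how the gap enters.** Let pH be the control proportion, pE the participants' own baseline proportion and e the true relative reduction.

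Apparent change = (pE / pH) × (1 − e) − 1

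With e = 0 this is gap / pH, where gap = pE − pH:

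| Clinic rate (assumed) | 3-point gap | 10-point gap |
|---|---|---|
| 30% | 3/30 = 10% | 10/30 = 33% |
| 42% | 3/42 = 7% | 10/42 = 24% |
| 60% | 3/60 = 5% | 10/60 = 17% |

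**Step 2: overlap.** If all 100 participants are also among 272 controls, the gap to the control mean is 172/272 = 63% of the gap to the remaining PLWD. Gaps of 3 and 10 points then mean that participants differ from the rest by 3/0.632 = 4.7 and 10/0.632 = 15.8 points. Overlap dilutes the gap but does not remove it.

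**Step 3: effect on the criterion.** The wording about the lower limit can be read in three ways:

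- A: the whole interval lies beyond a 25% decrease (upper limit of the ratio below 0.75).
- B: only the outer limit lies beyond it (lower limit of the ratio below 0.75).
- C: the lower limit of the ratio is above 0.75. This is the complement of B.

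Simulated chance of passing (400,000 draws, 272 against 100, independent groups, no clinic effect, interval on the log ratio, clinic rate 42%):

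| True effect | Gap (points) | A | B | C |
|---|---|---|---|---|
| None | −10 | 3% | 93% | 7% |
| None | 0 | <0.1% | 35% | 65% |
| None | +10 | <0.1% | 1% | 99% |
| 25% cut | −10 | 40% | >99% | 0.1% |
| 25% cut | 0 | 4% | 94% | 6% |
| 25% cut | +10 | 0.1% | 56% | 44% |

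Smaller gaps matter too. With no effect and a gap of −3 points, the chances are 0.1% (A), 56% (B) and 44% (C). Under each reading the result moves with the gap. A and B become easier to pass as participants start lower, and C becomes harder.

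**Step 4: limits of an own-baseline comparison.** Using participants' own earlier values removes pE / pH from the formula, but it is open to regression to the mean. If use before enrollment were 52% against a usual 42% (assumed), the return alone reads as 42/52 − 1 = −19%. In a paired simulation (n = 100, within-person correlation 0.5 assumed) with no DICE effect, reading B then passes 81% of the time, against 22% without the return. With a true 25% cut, reading A passes about half the time, against 4%.

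**The case against.** The strongest reply is that this is a feasibility pilot. Section 9.4 frames the primary clinical outcome as the feasibility of measuring psychotropic use, the Précis calls the comparison exploratory, and Section 9.5 concedes limited power. This stands as an argument on severity. It does not dispose of the point, because Section 9.5 still makes the result a condition for the ePCT.

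Second, the ambiguous confidence-limit wording moves the pass chance more than a modest gap does: with a true 25% cut and no gap, A gives 4% and B gives 94%. That is true, and it is a separate defect. The gap matters under every reading.

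Third, the Section 4.2 exclusion of non-English speakers is not assigned to a group and may cover controls. If so, the language difference goes. The care-partner and handoff differences remain.

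Fourth, an own-baseline estimate has its own bias, leaning toward a go decision. This stands and shapes the fix.

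Two stronger readings are tempting. A reader might infer that participants start with higher use, so that the contrast hides a benefit, because Section 2.1 says psychiatric medication is common practice for behavioral symptoms. The documents do not establish that net direction: dyads without symptoms are kept, electronic identification is also described, and the effect of the care-partner rule on use is not reported. A reader might also take the 10-point rows as likely. The documents neither support nor exclude a gap of that size.

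**Conclusion.** The comparison is not pre-post in the usual sense, and its estimate mixes any DICE effect with a baseline difference between two differently selected groups. That follows from Sections 4.1, 4.3, 6.2.1 and 9.5 and needs no assumed figure. The size does: at a clinic rate of 42%, gaps of 3 and 10 points read as 7% and 24% with no effect. The pass chances also rest on independent groups, 272 controls and the three readings. Secondary adjustment for unnamed covariates does not settle the matter, because the criterion is not tied to a model.

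Severity: should be fixed. It would be too strong to say that the flaw undermines the pilot, since the feasibility and acceptability aims do not depend on this contrast. Nor do the documents support replacing it with the own-baseline estimate as sole arbiter, which would exchange a bias of unknown sign for one that can favor proceeding.

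**What to change.** In Section 9.5:

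1. Restrict historical controls to the participant criteria readable from the EMR (listed care partner, English language). Link people who appear in both periods with a person-level term, and keep the clinic term.
2. Add a linked comparison of each participant's own EMR psychotropic use in windows of equal length before and after enrollment, reported as proportions because the benchmark is a relative decrease in a proportion. Do both analyses for utilization.
3. State in advance which model the second criterion uses. Do not let the crude unmatched contrast alone satisfy it, nor the own-baseline estimate alone, since secular trend and regression to the mean can favor a go. Either require the restricted-control and own-baseline estimates to be read together, or make the medication result supportive rather than a gate.
4. Use one control definition, either all PLWD or 100 with a stated selection rule, in the Précis and Sections 1.1, 3, 9.0 and 9.1.

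The confidence-limit wording needs its own correction.

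**Cost.** One EMR look-back for about 100 people; confirm that the requested waiver covers it. There will be fewer controls. The standard error of the log ratio for 42% against 31.5% is √(0.685/31.5 + 0.58/(0.42 × n0)). This is 0.164 with 272 controls, 0.168 with 218 (80% kept) and 0.179 with 136 (50% kept); the retained shares are assumed. The second criterion also becomes stricter or less decisive.
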